**Approval Period:** 12/11/2018 - 02/13/2019

Modification

1. Summarize your proposed changes.
 
1. Personnel Info
 
[name] was removed from Admin Contact and [name] was added as the new Admin Contact. We add under other personnel: [name] and [name].
 
Protocol Information
 
1. Purpose
 
Part A
 
It was updated (see the underlined text below) Repetitive Transcranial Magnetic Stimulation (rTMS) to Improve Cognitive Function in TBI: The proposed study will evaluate the safety, durability and efficacy of repetitive Transcranial Magnetic Stimulation (rTMS) as a promising non- invasive therapeutic treatment for executive function (EF)deficits and other outcomes (such as: headache, pain, etc) seen in 100 Veterans, Military personnel and Civilians with mild to moderate Traumatic Brain Injury (TBI).
 
Part B
 
Under Secondary Objective we added:
 
6. To evaluate improvement in headaches and pain reporting following rTMS treatment using responses on the assessment HIT-6 (HIT-6 has been included with the original protocol on Section 16)
 
2. Study Procedure
 
Please see the underlined text below (updates
 

• Headache and Pain self-report will be recorded before and after every treatment session.

 
8. Participant population
 
Please see the underlined text below (updates)
 

(i) 100 participants are expected to be enrolled

(ii) 100 participants at VAPAHCS

(iii) all participants will be Veterans, Military personnel and Civilians.

 
13. Consent
 
The consent was modified. See yellow highlighted sections.

2. Indicate Level of Risk
 
No Change

3. Update the Conflict of Interest (COI) section if any changes in COI have been made since the last protocol submission.
 
N Is there a change in the conflicting interest status for any existing personnel on this protocol?

Protocol Director		
Name [name]	Degree (Program/year if student) PhD	Position, e.g. Assistant Professor, Resident, etc. Clinical Assistant Professor (Affiliated) [VAPAHCS]

**Title :** Repetitive Transcranial Magnetic Stimulation to Improve Cognitive Function in TBI  
**Approval Period:** 12/11/2018 - 02/13/2019

**Participant Population(s) Checklist**

**Yes/No**

- Children (under 18) N
- Pregnant Women and Fetuses N
- Neonates (0 - 28 days) N
- Abortuses N
- Impaired Decision Making Capacity N
- Cancer Subjects N
- Laboratory Personnel N
- Healthy Volunteers N
- Students N
- Employees N

**Title :** Repetitive Transcranial Magnetic Stimulation to Improve Cognitive Function in TBI

**Approval Period:** 12/11/2018 - 02/13/2019

- Prisoners N
- Other (i.e., any population that is not specified above) Y

**Study Location(s) Checklist**

**Yes/No**

- Stanford University Y
  - Clinical & Translational Research Unit (CTRU) Y
  - Stanford Hospital and Clinics Y
  - Lucile Packard Children's Hospital (LPCH) Y
  - VAPAHCS (Specify PI at VA) Y
- [name] [name]
- Other (Click ADD to specify details)

**General Checklist**

**Multi-site**

**Yes/No**

- Is this a multi-site study? A multi-site study is generally a study that involves one or more medical or research institutions in which one site takes a lead role.(e.g., multi-site clinical trial) N

**Collaborating Institution(s)**

**Yes/No**

- Are there any collaborating institution(s)? A collaborating institution is generally an institution that collaborates equally on a research endeavor with one or more institutions. N

**Cancer Institute**

**Yes/No**

- Cancer-Related Studies (studies with cancer endpoints), Cancer Subjects (e.g., clinical trials, behavior/prevention) or Cancer Specimens (e.g., blood, tissue, cells, body fluids with a scientific hypothesis stated in the protocol). N

**Clinical Trials**

**Yes/No**

- Investigational drugs, biologics, reagents, or chemicals? N
- Commercially available drugs, reagents, or other chemicals administered to subjects (even if they are not being studied)? N
- Investigational Device / Commercial Device used off-label? Y
- IDE Exempt Device (Commercial Device used according to label, Investigational In Vitro Device or Assay, or Consumer Preference/Modifications/Combinations of Approved Devices) N
- Will this study be registered on# clinicaltrials.gov? ( See Stanford decision tree ) Y

**Title :** Repetitive Transcranial Magnetic Stimulation to Improve Cognitive Function in TBI

**Approval Period:** 12/11/2018 - 02/13/2019

- Is Stanford responsible for ClinicalTrials.gov registration? (See Stanford decision tree) NCT# N

**Tissues and Specimens**

**Yes/No**

- Human blood, cells, tissues, or body fluids (tissues)? Y
- Tissues to be stored for future research projects? Y
- Tissues to be sent out of this institution as part of a research agreement? For guidelines, please see <https://sites.stanford.edu/ico/mtas> N

**Biosafety (APB)**

**Yes/No**

- Are you submitting a recombinant DNA vector or Human Gene Transfer investigation using biological agents? If yes, please complete and attach the Gene Transfer Protocol Application Supplemental Questions to section 16 of the eProtocol application. N
- Are you submitting a Human study using biohazardous/infectious agents? If yes, refer to the <http://www.stanford.edu/dept/EHS/prod/researchlab/bio/index.html> Administrative Panel on BioSafety website prior to performing studies. N
- Are you submitting a Human study using samples from subjects that are known or likely to contain biohazardous/infectious agents? If yes, refer to the <http://web.stanford.edu/dept/EHS/prod/researchlab/bio/index.html> Administrative Panel on BioSafety website prior to performing studies. N

**Human Embryos or Stem Cells**

**Yes/No**

- Human Embryos or Gametes? N
- Human Stem Cells (including hESC, iPSC, cancer stem cells, progenitor cells) N

**Veterans Affairs (VA)**

**Yes/No**

- The research recruits participants at the Veterans Affairs Palo Alto Health Care System(VAPAHCS). Y
- The research involves the use of VAPAHCS non-public information to identify or contact human research participants or prospective subjects or to use such data for research purposes. Y
- The research is sponsored (i.e., funded) by VAPAHCS. N
- The research is conducted by or under the direction of any employee or agent of VAPAHCS (full-time, part-time, intermittent, consultant, without compensation (WOC), on-station fee-basis, on-station contract, or on-station sharing agreement basis) in connection with her/his VAPAHCS responsibilities. Y
- The research is conducted using any property or facility of VAPAHCS. Y

**Equipment**

**Yes/No**

**Title :** Repetitive Transcranial Magnetic Stimulation to Improve Cognitive Function in TBI

**Approval Period:** 12/11/2018 - 02/13/2019

- Use of Patient related equipment? If Yes, equipment must meet the standards established by Hospital Instrumentation and Electrical Safety Committee [contact]) N
- Medical equipment used for human patients/subjects also used on animals? N
- Radioisotopes/radiation-producing machines, even if standard of care? Y  
[http://www.stanford.edu/dept/EHS/prod/researchlab/radlaser/Human\\_use\\_guide.pdf](http://www.stanford.edu/dept/EHS/prod/researchlab/radlaser/Human_use_guide.pdf) More Info

**Payment**

**Yes/No**

- Subjects will be paid/reimbursed for participation? See payment considerations. N

**Funding**

**Yes/No**

- Training Grant? N
- Program Project Grant? N
- Federally Sponsored Project? Y
- Industry Sponsored Clinical Trial? N

**Funding**

Funding - Grants/Contracts	
Funding Administered By : VA	SPO # (if available) :
Grant # (if available) :	Funded By (include pending) : VA
Principal Investigator : [name]	
Grant/Contract Title if different from Protocol Title : _____	
Y	For Federal projects, are contents of this protocol consistent with the Federal proposal?
N	Is this a Multiple Project Protocol (MPP)?
N	Is this protocol under a MPP?

Funding - Fellowships
------------------------------

Gift Funding
---------------------

Dept. Funding
----------------------

Other Funding
----------------------

**Resources :**

- a) **Qualified staff.**

---

**Title :** Repetitive Transcranial Magnetic Stimulation to Improve Cognitive Function in TBI  
**Approval Period:** 12/11/2018 - 02/13/2019

---

**b) Training.**

**Describe the training you will provide to ensure that all persons assisting with the research are informed about the protocol and their research-related duties and functions.**

All staff, both present and future, will be trained in human subjects protections, computer security and privacy regulations.

All staff who administer the rTMS treatment will be fully trained and certified.

**c) Facilities.**

**Please describe and justify.**

The data will be collected at study visits at the VA Palo Alto Health Care System (VAPAHCS) War Related Illness and Injury Study Center (WRIISC). All collections will take place in the clinic setting. The data will be stored on VA servers administered by VA staff. The Data will also be analyzed on VA computers on VA networks. Some neuroimaging data will be analyzed on Stanford LAN connection.

**d) Sufficient time.**

**Explain whether you will have sufficient time to conduct and complete the research. Include how much time is required.**

This project is expected to last for 2 years. The duration of the study will be two years, with 18 month enrollment period, and the last six months will be strictly for follow-up. 20 participants will be recruited in the first year and 20 will be recruited in the second year. Each participant will be in the trial for a total of approximately 28 weeks (1-2 weeks screening, 2 weeks acute treatment phase (depending on scheduling constraints) and a follow-up visit at 26 weeks post-treatment. The last 6-8 months of the study will also be spent analyzing data and writing up results.

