**2. Study Procedures**

- a) **Please SUMMARIZE the research procedures, screening through closeout, which the human subject will undergo. Refer to sections in the protocol attached in section 16, BUT do not copy the clinical protocol. Be clear on what is to be done for research and what is part of standard of care.**

List of Procedures for the rTMS protocol:

Screening Measures:

- Telephone screening call: 1 hr
- Consenting and on-site screening: approx. 6 hrs
- Physical exam, medical history
- Medication review
- Interviews, self-report questionnaires  
Clinical TBI Evaluation
- Blood (60 cc), urine, and breath tests
- Determination of TMS motor threshold (markings on the cap will be marked with "MT" for motor threshold and "Tx" for treatment site.
- Eligibility determination
- Randomization to active or sham treatment

Baseline measures: approx. 8 hrs

- Interviews, self-report questionnaires, tasks (pain, fatigue, sleep, malingering, depression, PTSD, TBI, suicide, cognition);
- Cognitive testing (including main outcome measure for executive function) and webneuro computerized testing
- Neuroimaging: Diffusion Tensor Imaging (DTI), functional MRI (fMRI); structural MRI
- If indicated, and prior to MRI scan, an MRI X-ray screen will be performed if there is suspicion that participant may have metal in their body
- Pure Tone Audiometry

Intervention Measures:

- rTMS or sham treatment: up to 3 treatments a day for up to 5 days/week, 2-6 weeks = 20 sessions. Each session lasting 30-60 minutes in length. Depending on schedule, and at the physician's discretion, up to three rTMS sessions can be scheduled per day with a one hour interval between sessions, shortening treatment duration to 1.5 weeks.
- TMS motor threshold determination prior to the first treatment and every 5th day of treatment thereafter (at least weekly).
- Random breathalyzer and urine tests will be administered during the intervention phase to screen for drug and alcohol use; depending on results, participant may not be allowed to receive

**Title :** Repetitive Transcranial Magnetic Stimulation to Improve Cognitive Function in TBI  
**Approval Period:** 12/11/2018 - 02/13/2019

additional rTMS treatment for safety reasons

- Blood samples (60 cc) will be taken every 10 rTMS

treatment

for processing of BDNF from blood plasma.

- Headache and Pain self report will be recorded before and after every treatment session.

Follow-up (post treatment and 6 months): approx. 8.5 hrs

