**l) Costs. Please explain any costs that will be charged to the participant.**

**Title :** Repetitive Transcranial Magnetic Stimulation to Improve Cognitive Function in TBI  
**Approval Period:** 12/11/2018 - 02/13/2019

There are no costs to participants other than time and inconvenience.

**m) Estimate the probable duration of the entire study. Also estimate the total time per participant for: (i) screening of participant; (ii) active participation in study; (iii) analysis of participant data.**

Duration of the study: 2 years

Total time per participant for all screening: 7-8 hours.

For active participation in the study -

- Baseline: approximately 8 hours on-site with MRI, labs, clinical exams
- Intervention: approx. 30-60 minutes/session, 20 sessions over 2 -6 weeks, depending on scheduling
- Follow-up: one follow-up visits over 6 months, each visit lasting approx. 8.5 hrs

Analysis of participant data immediately post treatment and at 6 month follow-up

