**rTMS**

In the unlikely event that a seizure does occur, the participant will be closely monitored and treated for any medical or psychological consequences. Lab tests will be drawn and the participant will be seen by a neurologist as soon as possible. The facility where the rTMS studies are performed is fully equipped to safely handle a seizure. The participant will be given a letter regarding the seizure to share with his or her primary health care provider. The letter will indicate that the seizure during rTMS does not increase risk for future seizures.

rTMS treatment can result in mild to moderate headaches in as many as 30 out of 100 of patients. Some people also report discomfort at the site of rTMS stimulation. This occurs in around 15 out of 100 of patients. Headaches and site discomfort usually readily respond to acetaminophen or ibuprofen. Painfulness improves over time or goes away. Often patients fall asleep in the second week while receiving the same treatment that on the first day was reported as very painful.

There is a small risk of dental pain with rTMS, during or immediately after the treatment. If this occurs, study staff may be able to move the rTMS coil position or provide a bite block to reduce this pain or make it not happen.

rTMS treatment may produce movement or tingling of the arm, leg, face or scalp. Participants may also experience a temporary feeling of numbness in the face.

**Title :** Repetitive Transcranial Magnetic Stimulation to Improve Cognitive Function in TBI  
**Approval Period:** 12/11/2018 - 02/13/2019

There is a possible risk of hearing loss due to the light clicking sounds made by the device. Participants will wear earphones during rTMS sessions. This should greatly reduce the possibility of hearing loss. Hearing will be tested at baseline, after the intervention phase, and after follow-up to see if any hearing loss has occurred.

The rTMS operator will monitor all participants for ear protection, coil placement, and seizure activity during all sessions.

- d) Explain the point at which the experiment will terminate. If appropriate, include the standards for the termination of the participation of the individual participant Also discuss plans for ensuring necessary medical or professional intervention in the event of adverse effects to the participants.**

The clinical trial will terminate after 2 years or when 40 participants have been through the protocol.

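### The two-year timetable does not close: the six months after enrolment ends hold only the 26-week follow-up interval, with no room for late entrants' screening and treatment, and the 28-week participant time leaves screening out

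*Protocol*

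**What the plan says.** Resources, item d (Sufficient time) sets the calendar: "The duration of the study will be two years, with 18 month enrollment period, and the last six months will be strictly for follow-up". The same item gives the time per participant, "Each participant will be in the trial for a total of approximately 28 weeks", and lists its parts as "1-2 weeks screening, 2 weeks acute treatment phase (depending on scheduling constraints) and a follow-up visit at 26 weeks post-treatment".

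Two other sections describe the treatment phase differently. Section 2a has "up to 3 treatments a day for up to 5 days/week, 2-6 weeks = 20 sessions" and adds that several sessions a day are possible, "shortening treatment duration to 1.5 weeks". Section 8m has "20 sessions over 2 -6 weeks, depending on scheduling", and also gives the study duration as two years.

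Section 9d states when the trial stops: "The clinical trial will terminate after 2 years or when 40 participants have been through the protocol". Section 8g gives the accrual plan of 2.2 patients per month, to reach 40 in 18 months.

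**The concern.** There are two separate faults in the same item.

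The first is in the calendar. The follow-up-only period is about as long as the interval from end of treatment to the last visit. Anyone enrolled near month 18 must still be screened and treated before that interval starts, and the timetable leaves no time for this.

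The second is in the participant time. The total of 28 weeks does not include the screening listed beside it, and it does not reflect the treatment ranges in Sections 2a and 8m.

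What is at stake is the 6-month visit. Durability of benefit is part of the specific aim, and secondary hypothesis 1 and secondary objective 1 depend on that visit. A timetable that can cut it off for the last entrants creates missing data through the calendar, whatever the retention.

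**Working it through.** **Inputs.** Screening 1-2 weeks, treatment 2 weeks, last visit 26 weeks post-treatment, enrolment 18 months, study 24 months (all Resources d). Treatment 1.5 weeks at the shortest (Section 2a) and up to 6 weeks (Sections 2a and 8m). Accrual 2.2 per month (Section 8g).

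**Step 1: the plan's own figure.** Treatment + follow-up = 2 + 26 = 28 weeks. The stated total is reproduced exactly, but only with screening left out.

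**Step 2: all listed parts.** Screening + treatment + follow-up:
- 2-week treatment: 1 + 2 + 26 = 29 to 2 + 2 + 26 = 30 weeks (3.6% to 7.1% above 28)
- 1.5-week treatment: 1 + 1.5 + 26 = 28.5 to 2 + 1.5 + 26 = 29.5 weeks
- 6-week treatment: 1 + 6 + 26 = 33 to 2 + 6 + 26 = 34 weeks (18% to 21% above 28)

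**Step 3: time left after enrolment closes.** Weeks per month = 365.25 / 7 / 12 = 4.348. Six months = 6 × 4.348 = 26.1 weeks.

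**Step 4: overrun for a month-18 entrant.** Overrun = total − 26.1 weeks. Latest entry that fits = 24 − total / 4.348 months. Participants affected = (overrun / 4.348) × 2.2, with uniform accrual up to month 18.

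| Total (weeks) | Overrun (weeks) | Latest entry (month) | Affected, of 40 |
|---|---|---|---|
| 28 (as stated, no screening) | 1.9 | 17.6 | 1.0 |
| 28.5 | 2.4 | 17.5 | 1.2 |
| 29 | 2.9 | 17.3 | 1.5 |
| 29.5 | 3.4 | 17.2 | 1.7 |
| 30 | 3.9 | 17.1 | 2.0 |
| 33 | 6.9 | 16.4 | 3.5 |
| 34 | 7.9 | 16.2 | 4.0 |

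The first row counts enrolment from the first treatment session; the others count from the start of screening. The most favourable corner, 1.5-week treatment counted from the first session, is 1.5 + 26 = 27.5 weeks. It still overruns by 27.5 − 26.1 = 1.4 weeks, or (1.4 / 4.348) × 2.2 = 0.7 participants.

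**Step 5: sensitivity to accrual.** Resources d also plans 20 participants in each year. With enrolment closing at month 18, the second 20 would enter in six months, 20 / 6 = 3.3 per month. The count then runs from (1.9 / 4.348) × 3.3 = 1.5 to (7.9 / 4.348) × 3.3 = 6.1 of 40. The accrual pattern is not settled in the protocol, so this is a range and not a correction.

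**The case against.** The best defence is that the figures are planning estimates. The 28 weeks is given as approximate, equals treatment plus follow-up exactly, and is only 1-2 weeks short on the 2-week schedule. That stands: on that schedule the figure is loosely stated rather than badly wrong. It does not cover the 5-6 week gap with 6-week treatment.

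Three stronger readings are tempting, and the documents do not support them.

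- *The understated 28 weeks causes the overrun.* It does not. Twenty-eight weeks already exceeds the 26.1 weeks available, so correcting it to 29-30 would neither create nor remove the problem. The cause is the length of the follow-up-only window.
- *Late entrants are bound to lose the 6-month endpoint.* This is not shown. Section 9d joins two conditions with an *or* and does not say which governs; completing the protocol can be read to include the 6-month visit. Resources d only expects the project to last two years, and nothing says that visits already due would be cancelled. The attachments date from 2014 and 2015, while this version's approval period is December 2018 to February 2019. That suggests two years has not worked as a hard limit, although the start of enrolment is not given.
- *The loss scales up to the 100 participants now expected.* The protocol ties the 18-month window and the termination rule to 40 participants and gives no accrual rate for 100. The conflict between 40 and 100 is a separate matter and is not used here.

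The upper end of the range also needs every late entrant to take the full six weeks of treatment.

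**Conclusion.** The timetable is wrong as written, but the consequence is small. Under every combination checked, a month-18 entrant's final visit falls after month 24, by about 2 to 8 weeks (1.4 weeks in the most favourable corner). If the two-year limb of Section 9d governs, about 1-4 of 40 participants would miss the 6-month durability visit. This assumes uniform accrual at 2.2 per month up to month 18.

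Separately, the participant time should read about 28.5-34 weeks once screening and the permitted treatment durations are counted. The primary hypothesis compares baseline with post-treatment and is not affected. This is a minor correction that protects a secondary endpoint.

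**What to change.** 1. In Resources d, restate the time per participant to include screening and the permitted treatment window: about 28.5-34 weeks on the durations now in the protocol.
2. Reconcile the treatment durations in Resources d, Section 2a and Section 8m. Which duration applies is for the investigators to settle; the total in item 1 follows from it.
3. In Section 9d, define the end of the trial as the last randomised participant's 26-week post-treatment visit, and say how the two-year and 40-participant conditions relate to it.
4. If two years is fixed, close entry at about month 16 instead (24 − 34 / 4.348 = 16.2).

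Items 1 to 3 cost wording plus up to about two more months of follow-up (7.9 weeks = 1.8 months). Item 4 costs about two months of enrolment, so reaching 40 would need 40 / 16 = 2.5 participants per month instead of 2.2.

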**e) Access to target population.**

**Explain and justify whether you will have access to a population that will allow recruitment of the required number of participants.**

**Title :** Repetitive Transcranial Magnetic Stimulation to Improve Cognitive Function in TBI  
**Approval Period:** 12/11/2018 - 02/13/2019

The WRIISC is a national referral center established to further diagnosis and provide treatment options for veterans suffering from military related injuries and illnesses. We have seen a number of local Veterans from various conflict eras with TBI through our clinic locally. Our collaboration with [name], who works in VAPAHCS polytrauma center will also provide us with study participants. We are confident that there are a sufficient number of Veterans with mild and moderate TBI in the Northern CA area.

